3 STUDY DESIGN

3.1 STUDY DESIGN AND RATIONALE

This phase 3 study is a randomized, observer-blinded, comparator controlled study of Seqirus QIV, administered intramuscularly into the deltoid region or the anterolateral aspect of the thigh, versus a US licensed comparator QIV containing the same influenza strains recommended by the the US Food and Drug Administration (FDA) and Vaccines and Related Biological Products Advisory Committee (VRBPAC) for the 2016-2017 season. The study will be conducted during the 2016-2017 Northern Hemisphere influenza immunization season in male and female subjects 6 months through 59 months of age.

After parent(s)/guardian(s) have provided written informed consent (Visit 1 [Day 1]), eligible subjects will be stratified by age to one of two age cohorts:

- Cohort A comprising subjects 6 months through 35 months of age;
- Cohort B comprising subjects 36 months through 59 months of age.

The Interactive Response Technology (IRT) will include a quota for each age stratum so that no more than 60% of the total sample size is represented in each age stratum.

Subjects in the 36 through 59 months age group will be enrolled and randomized first until approximately one third of subjects (or a minimum of 300 subjects) in this age cohort have received the first vaccination and have had an opportunity to enter at least 7 days of safety data postvaccination. A safety data cut will then be performed, tables and listings produced and a Data and Safety Monitoring Board (DSMB) meeting convened to review and assess the available safety data.

Recruitment in the 36 through 59 months age cohort will not be halted during the period of the data cut and DSMB review. Enrollment in the younger age cohort (subjects 6 months through 35 months of age) will only commence after the DSMB has reviewed the safety data and recommended that the study may proceed.

A second safety data cut will be performed when approximately one third of subjects (or a minimum of 300 subjects) in the 6 through to 35 months age cohort have received the first vaccination and have had an opportunity to enter at least the 7 days of safety data postvaccination. A DSMB meeting will be convened once tables and listings are produced to review and assess the available safety data. Recruitment in the 6 through 35 months age cohort will not be halted during the period of the data cut and DSMB review.

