After stratification, subjects will be randomized to one of the two treatment groups using a 3:1 allocation ratio to receive either Seqirus QIV or the US licensed comparator QIV ([Figure 1](#)).

Subjects will provide pre- and postvaccination serological specimens as well as structured safety follow-up.

Screening evaluations will be performed either the day of the vaccination or within a maximum of 1 week before vaccination and include medical history, and targeted physical examination (if clinically indicated). Vaccination will occur on Day 1. On Day 1 and prior to vaccination, a serum sample will be collected for influenza-specific serology.

The preferred sites for intramuscular injection are the anterolateral aspect of the thigh in infants 6 months through 11 months of age, the anterolateral aspect of the thigh (or the deltoid muscle if muscle mass is adequate) in children 12 months through 35 months of age, or the deltoid muscle of the non-dominant arm in children 36 months through 59 months of age.

The parent(s)/guardian(s) of subjects will record electronically:

[figure not shown]
1. In a “7-Day Diary”, the occurrence of solicited AEs, a pre-specified series of local reactions and systemic symptoms and temperature that may occur between Day 1 and Day 7 after a vaccination.
2. In an “Other Body Symptoms Diary”, any unsolicited AEs that may occur between Day 1 and the Study Exit Visit.
3. In a “Medication Diary”, all concomitant medication use that may occur between Day 1 and the Study Exit Visit.

Subjects will return to the clinic 28 (+4) days after each indicated vaccine dose (Day 29 +4). During this visit, entries in the 7-Day Diary, the Other Body Symptoms Diary and the Medication Diary will be reviewed with the parent(s)/guardian(s) and a targeted physical examination performed as clinically indicated. For one-dose schedule subjects, Visit 2 (Day 29+4) post vaccination is the Exit Visit ([Figure 2](#)). For two-dose schedule subjects, Visit 3 (Day 29+4 post second vaccination) is the Exit Visit ([Figure 3](#)). SAEs and adverse events of special interest (AESIs) will be collected via a telephone call at least 90 days after the last vaccination dose (Day 90+7) and another at 180 days after the last vaccination dose (Day 180+7).

Analyses of safety data may be triggered by the DSMB if halting rule criteria are met in either study age cohort, or following ad-hoc requests for review by Seqirus as described in the DSMB Charter.

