3.3 PLANNED STUDY DURATION

Study subjects will be scheduled to receive either a single vaccination or two-vaccination regimen as clinically indicated.

The maximum study duration for an individual subject receiving a single vaccination will be up to 7 months (up to 7 days screening period, 28+4 days active study period and 180+7 days safety follow-up period).

The maximum study duration for an individual subject scheduled for the two-vaccination regimen will be up to 8 months (up to 7 days screening period, 28+4 days active study period after each Study Vaccine dose, and 180+7 days safety follow-up period after the last vaccination dose).

The overall study duration (ie, first subject's screening visit to last subject's end of study visit) will be a maximum of 10 months.

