3.6 STUDY MONITORING PROCEDURES

3.6.1 Data and Safety Monitoring Board

An independent DSMB will monitor subject safety during the study. The DSMB will comprise clinical study experts with experience in vaccine studies and safety assessment. The DSMB will provide recommendations for stopping or continuing the study based on the assessment of study safety data according to processes defined in the study protocol and the DSMB Charter.

DSMB will review available safety data and provide recommendations after approximately one third of subjects (or a minimum of 300 subjects) in the 36 through 59 months age group have received the first vaccination and have had an opportunity to enter at least 7 days of safety data postvaccination.

A second safety data cut will be performed when approximately one third of subjects (or a minimum of 300 subjects) in the 6 through to 35 months age cohort have received the first vaccination and have had an opportunity to enter at least 7 days of safety data postvaccination. A DSMB meeting will be convened once tables and listings are produced to review and assess the available safety data. Recruitment in both age cohorts will not be halted during the period of the data cut and DSMB review.

Adverse events contributing to enrollment halting rules (see [Section 9.7](#)) will be reported to the Sponsor automatically from the electronic Case Report Form (eCRF) in the clinical database. If enrollment halting rules are met, enrollment into the study will be halted pending DSMB review of the safety data, and Sponsor consideration of DSMB recommendations following the review. Independent safety monitors at each site are not required.

The DSMB will:

- Be responsible for providing recommendations to Seqirus surrounding study conduct matters that affect safety.
- Review the safety data at designated time points and potentially ad-hoc time points and identify if significant safety concerns arise during the study.
- Review data that may affect subject continuation.
- Make recommendations regarding study progression.

The DSMB will be constituted and conducted in accordance with the FDA *Guidance for Clinical Trial Sponsors. Establishment and Operation of Clinical Trial Data and Monitoring Committees. March 2006.*

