9.7 OTHER SIGNIFICANT EVENT REPORTING - ENROLLMENT HALTING RULES

An independent Data Safety Monitoring Board (DSMB) will monitor subject safety during the study. The DSMB will comprise clinical study experts with experience in vaccine studies and safety assessment. The DSMB will provide recommendations for stopping or continuing the study based on the assessment of study safety data according to processes defined in the study protocol and the DSMB Charter.

Enrolment into the study and study vaccination will be halted for DSMB review/ recommendation for continuation if during the 7 days after vaccination (Day 1 to Day 7) any of the following occur:

- One or more subject experiences an AE that is serious, unexpected, and is assessed as related to Study Vaccine;
- One or more subject experiences an AE that is life-threatening or causes death;
- One or more subject experiences a serious febrile AE, defined as any AE meeting seriousness criteria that is also associated with a fever of $\geq 101.3^{\circ}\text{F}$ / $\geq 38.5^{\circ}\text{C}$ (axillary).
- One or more of the subjects experiences a severe (grade 3)
 - allergic reaction (eg, hives, angioedema, allergic asthma, systemic anaphylaxis);
 - Vaccine-related injection site ulceration, abscess, or necrosis;

Additionally, enrolment into the study and study vaccination will be halted pending review by the DSMB if during Day 1 to Day 7, the following defined halting rule criteria are met in either study cohort (6 months through 35 months or 36 months through 59 months):

- $\geq 5\%$ of subjects enrolled to date, with concurrent grade 3 pain, erythema, and induration (a cellulitis-like reaction) that is assessed as related to Study Vaccine.

(Note: If the total number of subjects enrolled to date is less than 60, a minimum of 3 subjects experiencing a concurrent severe vaccine-associated pain, erythema or induration will be needed to halt further enrolment);

- $\geq 5\%$ of subjects enrolled to date experience a fever of $\geq 101.3^{\circ}\text{F}$ / $\geq 38.5^{\circ}\text{C}$ (axillary) that is assessed as related to Study Vaccine.

(Note: if the total number of subjects enrolled to date is less than 60, a minimum of 3 subjects is required to trigger the halt).

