In addition, the DSMB chair will be immediately notified of any SAE, regardless of causality or expectedness assessment, occurring during Day 1 to Day 7. The DSMB chair will then make a determination regarding the necessity of a DSMB meeting and/or study halt in response to these events.

Any decision to terminate the study will be made by Seqirus in consultation with the DSMB, and the study investigators.

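### The protocol requires immediate notice to the DSMB chair only for events on Days 1 to 7 after a vaccination; a later death, AESI or related SAE need not reach the board promptly while dosing continues

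*Protocol*

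**What the plan says.** Protocol section 9.7, repeated in the synopsis, sets out three safeguards.

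- **Single-event halts.** Enrollment and vaccination stop for DSMB review "if during the 7 days after vaccination (Day 1 to Day 7) any of the following occur". The list covers related unexpected serious events, life-threatening or fatal events, serious febrile events, severe allergic reactions, and vaccine-related ulceration, abscess or necrosis at the injection site.
- **Two 5% rules** per age cohort, for cellulitis-like reactions and for fever of at least 38.5°C, also limited to Days 1 to 7.
- **Notice to the chair.** "the DSMB chair will be immediately notified of any SAE, regardless of causality or expectedness assessment, occurring during Day 1 to Day 7". The chair then decides whether a meeting or a halt is needed.

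Section 3.6.1 schedules two DSMB reviews, one per cohort, each when about one third of the cohort (or at least 300 children) has had a first dose and a chance to enter 7 days of data. Under section 3.1, enrollment of the 6-35 month cohort "will only commence after the DSMB has reviewed the safety data and recommended that the study may proceed". Recruitment is not paused during either review.

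The other ways for a case to reach the board are permissive or conditional. Safety analyses may be triggered if halting criteria are met or "following ad-hoc requests for review by Seqirus as described in the DSMB Charter" (section 3.1). The board's listed duties include: "Review the safety data at designated time points and potentially ad-hoc time points" (section 3.6.1). SAP section 4.2 says that halting-rule triggers may lead to further review under the Charter. Section 9.7 adds: "Any decision to terminate the study will be made by Seqirus in consultation with the DSMB" and the investigators.

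SAEs and AESIs are collected until 180 days after the last dose (section 9.4) and are reported to the sponsor within 24 hours (sections 9.1.2 and 9.6).

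**The concern.** The rules drop sharply at Day 8. A life-threatening event on Day 7 halts the whole study automatically. The same event with onset on Day 8 does not oblige anyone to tell the DSMB chair, even though other children may be due a first or second dose the next day.

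The plan itself treats later events as important. The AESI list includes Guillain-Barré syndrome, transverse myelitis and febrile convulsion, all followed to Day 180. Section 7.1 bars a second dose after a related seizure without any seven-day limit, but only for the affected child. The DSMB reviews unblinded safety data in closed session while the sponsor's team stays blinded (section 6.1.3.3), so the board is well placed to judge whether a late event should affect the children still to be dosed. As written, whether it hears of such an event promptly depends on the sponsor's discretion. This is also the first study of this vaccine at this age (section 1.4), in the age group where most of the 2010 febrile reports arose (section 1.1.2).

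**Working it through.** The plan gives no figure on this point, so there is none to reproduce. The check is mainly of the text, with some arithmetic for scale.

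**1. Routes for an event with onset on Day 8 or later**

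| Route | Where | Open from Day 8? | Mandatory prompt notice to the DSMB? |
|---|---|---|---|
| Single-event halts | 9.7, synopsis | No | – |
| 5% cohort rules | 9.7, synopsis | No | – |
| Immediate notice to chair | 9.7, synopsis | No | – |
| Two scheduled reviews | 3.6.1 | Yes, for data available at the cut | No: timed by enrollment, not by the event |
| Ad-hoc review | 3.1, 3.6.1 | Yes | No: discretionary |
| Consultation on termination | 9.7 | Yes | No: only if termination is being decided |
| 24-hour report | 9.6, 9.1.2 | Yes | No: goes to the sponsor |
| IRB report | 9.6.1, 9.8 | Yes | No: goes to the IRB |
| SUSAR report | 6.1.3.3 | Yes | No: goes to regulators |
| Bar on second dose | 7.1 | Yes for some related events | No: affected child only |

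No row combines an open route, a mandatory duty and prompt notice to the DSMB. This is equally true before the first cut, between the cuts and after the second. The table reads Days 1 to 7 as restarting after a second dose, which is the more protective reading.

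**2. Days between doses outside the rules.** The second dose is given 28 (+4) days after the first (section 8.4.2). That leaves 28 − 7 = 21 days, or 32 − 7 = 25 days at the end of the window.

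**3. How long dosing can last.** The study lasts at most 10 months (section 3.3), or 10 × 365/12 = 304 days. Follow-up after the last dose is 180 (+7) days. Dosing must therefore end by day 304 − 187 = 117 to day 304 − 180 = 124 after the first screening.

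**4. First doses outstanding at the second trigger.** About 2222 children are planned, with no more than 60% in either stratum (section 3.5). The younger cohort is therefore between 0.40 × 2222 = 889 and 0.60 × 2222 = 1333. Taking the trigger as one third of the cohort, but at least 300:

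- 889 children: 889/3 = 296, so 300 applies; 889 − 300 = 589 remain (66%).
- 1333 children: 1333/3 = 444; 1333 − 444 = 889 remain (67%).

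These are counts at the trigger. Fewer remain once recruitment during the 7-day wait, the data cut and the review is allowed for. Second doses, and any remaining doses in the 36-59 month cohort, come on top and cannot be counted from the documents. All these children stay under the Day 1-7 rules.

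**The case against.** The strongest objection is that the rule may sit in the DSMB Charter. The protocol assigns the board's processes jointly to itself and the Charter, and the SAP refers the DSMB analysis there. A duty to forward late events could properly be in that document. This stands: the documents show that the duty is not in the protocol or SAP, not that the trial lacks it.

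Second, a reader might infer that late events escape independent oversight. The documents do not support that. Investigators must report all SAEs to the IRB whatever the day (section 9.6.1), section 9.8 covers IRB notice of deaths and unexpected product-related SAEs, and SUSARs can be unblinded individually for expedited reporting to regulators. Sponsor safety staff review every AESI for signals, and the sponsor may suspend the study at any time (section 14.6). The board also has a general duty to monitor safety throughout. None of this sets a duty to notify the board promptly, but it narrows the point to that one duty.

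Third, the seven-day window has a rationale. The documented product risk is acute, namely fever and febrile seizures through a cytokine response (section 1.1.2), and within Days 1 to 7 the rules are strict. The documents identify no specific later-onset risk of this vaccine. That supports keeping the halting rules as they are. It does not explain why the chair need not be told of a related SAE, an AESI or a death after Day 7 while dosing continues.

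**Conclusion.** The point holds in a limited form: neither the protocol nor the SAP requires prompt notice to the DSMB of a death, AESI or vaccine-related SAE with onset on Day 8 or later, at any time during dosing. Data collection, sponsor reporting and the primary analysis are unaffected.

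Two stronger readings should be avoided. One is that no route to the board remains after the second review; the Day 1-7 rules and ad-hoc reviews continue. The other is to forecast the number of late events from the adult study in section 1.2.3, which reported 6 deaths and 3 subjects with related SAEs among 3485. That study included people aged 65 and over, and its one related death was in that group, in a subject with existing lung disease. Those rates do not carry over to generally healthy children, and the documents give no AESI rate. The number of added notices therefore cannot be estimated, though it should be small.

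The 589 to 889 children show how much first dosing could still lie ahead at the second trigger. The range assumes the planned total, a 40% to 60% share for the younger cohort and a trigger at one third (at least 300). It is an upper figure for each cohort size under those assumptions, and it is not a count of children harmed or unprotected. The conclusion is also subject to the Charter.

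**What to change.** Keep the Day 1-7 halting rules and the Day 1-7 notice of any SAE unchanged. Add one sentence to section 9.7 and the synopsis:

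> *Until the last study vaccination has been given, the DSMB chair will also be immediately notified of every death, every AESI and every SAE assessed as related to Study Vaccine, whatever the day of onset.*

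The chair keeps the existing discretion to call a meeting or halt the study. If the Charter already requires this notice, a cross-reference in section 9.7 is enough.

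This is a cheap improvement. It uses reports that already reach the sponsor within 24 hours, needs no new data and creates no new automatic halt. The downside is a few extra notices to the chair.

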9.7.1 Overdose

Details (ie, volume, location of injection) of overdose of the investigational product or any concomitant therapy must be recorded in the eCRF. Any overdose that is considered by the Investigator to be medically significant must be reported as an SAE, see [Section 9.6](#) (Serious Adverse Event Reporting).

9.7.2 Pregnancy and Lactation

Not applicable.

9.8 IRB / IEC REPORTING REQUIREMENTS

The time frame within which an IRB must be notified of deaths and investigational product-related unexpected SAEs is stipulated by each IRB. It is the Investigator's responsibility to comply with the requirements for IRB notification. Seqirus will provide Investigators with all details of all SAEs reported to regulatory authorities.

9.9 FOLLOW-UP OF ADVERSE EVENTS

Every effort should be made to follow-up subjects who continue to experience an AE or an SAE on completion of the study until either the AE resolves or stabilizes, whichever is sooner. All follow-up information (and attempted follow-up contacts) should be documented in the subject's medical records. Details of SAE follow-up should also be submitted to Seqirus Safety.

10 ASSESSMENTS

10.1 SUBJECT CHARACTERISTICS

Subject characteristics to be evaluated will include:

- Demographic data (eg, date of birth, age, sex, race, ethnicity)
- Medical history and documentation of relevant medical history, defined as 1) any current medical condition ongoing at the time of signing ICF; 2) any recent or past medical history, which in the opinion of Investigator would potentially have an impact on subject's eligibility, study safety or immunogenicity outcomes. Relevant medical history can also include any medical history that contributes to the understanding of an AE that occurs during study participation, if it represents an exacerbation of an underlying disease/preexisting problem.
- Influenza vaccination history
- Body weight and axillary temperature
- Current/concomitant therapies.

10.2 EFFICACY (IMMUNOGENICITY) ASSESSMENTS

Efficacy assessment involves the assessment of immunogenicity on the basis of HI antibody titer to each strain, performed on serum specimens taken at Day 1 (Visit 1) and at the Study Exit Visit (Visit 2 – single dose schedule or Visit 3 – two-dose schedule).

Immunogenicity will be expressed as:

- *HI antibody titer for each strain:* All analyses involving HI antibody titer (namely GMT within a treatment group) will be based on the log scale and the resultant summary statistic back-transformed to derived GMT;
- *Seroconversion:* For each strain the subjects will be classified as 'seroconverted' if either they have a prevaccination HI antibody titer < 1:10 and a postvaccination HI antibody titer \geq 1:40 or a prevaccination HI antibody titer \geq 1:10 and a \geq 4-fold increase in postvaccination HI antibody titer. Otherwise they will be classified as 'not seroconverted';
- *Seroprotection:* For each strain a subject will be classified as 'seroprotected' if their HI antibody titer \geq 1:40 at Days 1 and the Study Exit Visit. If they do not have both antibody titers \geq 1:40 they will be classified as 'not seroprotected';
- *Fold increase:* For each strain the fold increase for each subject will be calculated by taking the ratio of the postvaccination antibody titer over the prevaccination antibody titer;
- Covariate adjusted analyses will be performed as outlined in the Statistical Analysis Plan (SAP)

10.3 SAFETY ASSESSMENTS

Safety will be assessed through solicited local reactions, solicited systemic AEs, unsolicited AEs and SAEs.

Type, frequency and intensity of solicited local reactions through to Day 7 (Day 1, 2, 3, 4, 5, 6, 7) following each study vaccination dose. These include pain, induration/swelling, and erythema/redness.

Frequency of cellulitis-like reaction for 28 days following vaccination. Cellulitis-like reaction is defined as the concurrent presence of grade 3 injection site pain, erythema/redness and induration/swelling.

Type, frequency, duration and intensity of solicited systemic AEs through to Day 7 (Day 1, 2, 3, 4, 5, 6, 7) following each study vaccination dose. These include headache, malaise and fatigue, myalgia, fever, diarrhea, and nausea and/or vomiting for children 36 months through 59 months of age, and fever, diarrhea, nausea and/or vomiting, loss of appetite, and irritability for children 6 months through 35 months of age.

Frequency of antipyretic use in the 7 days after each vaccination dose.

Type, frequency, duration and intensity of unsolicited AEs for at least 28 days following each study vaccination dose.

Frequency of SAEs and AESIs for at least 180 days following vaccination.

